## 7 MATERIALS AND SUPPLIES

### 7.1 Study Medication

Deferiprone:

Deferiprone will be supplied to the clinical sites by ApoPharma Inc. as 500 mg film-coated scored tablets and/or 80 mg/mL oral solution. It will be manufactured by Apotex Inc., Toronto, Ontario, Canada, and will have been tested and released according to appropriate standards and regulations.

Deferoxamine:

Deferoxamine will be obtained from Hospira Inc. It will be provided by ApoPharma Inc. to the clinical sites as 2 g vials of sterile deferoxamine mesylate. The vials are to be stored as per label requirement, and their contents are to be dissolved according to the instructions provided by the investigator or qualified designate.

### 7.2 Packaging and Labelling

Study medication will be supplied by the Sponsor to the Investigator for each patient enrolled and randomized in the clinical trial. Study medication provided must only be used to treat patients enrolled in this clinical trial.

Ferriprox tablets will be supplied in bottles of 100 tablets each, high-density polyethylene (HDPE) bottles with child-resistant closure and appropriately labelled. Deferiprone 80 mg/mL oral solution will be supplied in 250 mL bottles with child-resistant closure and appropriately labelled.

Deferoxamine will be supplied in vials of 2 g and appropriately labelled.

The contents of the label will be in accordance with all applicable regulatory requirements. The label will include protocol number, expiry date, lot/batch number, investigational statement, storage temperature, dosage, direction for use, visit number, and name and address of the Sponsor.

### 7.3 Storage and Disposition of Study Medications

The study medication will be stored in a locked room/cabinet at each site. The supply of study medication will be stored as per label requirements in a secure location under the control of the Investigator. The Sponsor will provide a digital temperature monitoring device (if required) and a temperature log to facilitate daily recording of the temperature

of the study medication storage facility. The site must report temperature deviations immediately to the Sponsor and quarantine the product until the Sponsor deems it acceptably for human use.

## 7.4 Drug Dispensing Procedures

Dispensing of study medication is to be done by appropriately qualified staff (e.g., physician, pharmacist, or nurse).

At the baseline visit, any patient for whom all necessary dosage information is available will be dispensed enough study medication for the next 4 weeks. However, if (1) a patient's baseline serum ferritin result is not yet available, AND (2) a higher dosage is not indicated on the basis of the other iron overload markers (transfusional iron input, LIC, and cardiac MRI T2\*), dispensing will be done as follows:

For patients randomized to DFP: All participants will be dispensed a 3-week supply of medication based on the scheduled titration (15 mg/kg tid for the first week, 20 mg/kg tid for the second week, and 25 mg/kg tid for the third week). At the Week 3 visit, at which time the baseline serum ferritin results will be available, they will be dispensed a 1-week supply at either 25 or 33 mg/kg tid as appropriate.

For patients randomized to DFO:

- If a serum ferritin value from within the last 3 months is available, the patient will be dispensed enough medication for 1 week based on that earlier value, and must continue to be dispensed the same dose on a weekly basis (i.e., returning to the site each time for the next week's supply) until the baseline serum ferritin result is available. Once it is available, the dosage will either be left as is or adjusted accordingly.
- If no serum ferritin value has been obtained within the last 3 months, the start of DFO dosing **must be deferred** until the baseline result is available.

At the Week 4 visit and thereafter, medication will be dispensed monthly for all patients.

Patients reporting that their medication has been lost or misplaced will be asked to attend the study site to receive replacement medication. Requests for replacement must be made in writing to the Sponsor's Project Leader (PL), Clinical Research by the appropriate clinical site (pharmacist/physician/Investigator), who will approve the request. The replacement will then be made through the IVRS system by the study coordinator. All information related to the lost/misplaced medication and the replacement medication must be recorded in the drug accountability forms.

## 7.5 Study Medications Accountability and Inventory Control

A "Site Investigational Drug Inventory Record" and "Patient Investigational Drug Dispensing Record" form will be provided by the Sponsor to the Investigator.

Investigational product accountability lies with the Investigator at all times. The Investigator must maintain an updated Site Investigational Drug Inventory Record at the study site. This log will include at minimum:

- Name of Sponsor
- Name of Investigator
- Study identifier
- Date and quantity of investigational product received from Sponsor
- Lot/Batch number

For each patient, the Investigator must maintain an updated Patient Investigational Drug Dispensing Record. This log will include at a minimum:

- Patient identification number
- Date of dispensing and return
- Dispenser's initials
- Quantity dispensed and returned

At the conclusion of the study, a final inventory must be performed by the Investigator (or delegate). If any tablets are missing, this must be indicated on the study drug accountability form, together with an explanation of the discrepancy. These forms must be available for Sponsor clinical monitoring as well as for Sponsor audit and regulatory authority inspection purposes at any time.

All investigational products that have been returned by the patient or that are unused for any other reasons will be returned to the Sponsor or discarded by the site according to internal procedures, which must include the issuance of appropriate signed destruction certificates including mode of destruction and complete drug accountability of destroyed materials.

## **7.6 Other Study Supplies**

All required study supplies including but not limited to infusion pumps, diary cards and laboratory kits will be provided to all sites.

# **8 MEASUREMENTS AND EVALUATIONS**

Efficacy and safety measurements/evaluations will be performed at visits outlined in Appendix 18.1 – Schedule of Study Procedures.

## **8.1 Efficacy**

### **8.1.1 Primary Efficacy Measure**

#### **8.1.1.1 Liver Iron Concentration**

The liver contains 70% or more of total body iron (Angelucci E *et al.* 2000), justifying the use of liver iron concentration (LIC) as a measure of body iron load (Brittenham GM *et al.* 2001; Olivieri NF & Brittenham. 1997; Overmoyer BA *et al.* 1987; St Pierre TG *et al.* 2005). In the absence of effective iron chelation therapy, transfusion-dependent patients experience a progressive increase in LIC (Cazzola M *et al.* 1983). Although liver iron concentrations may differ from the concentrations of iron in other organs, it has been reported that patients with LIC greater than 7 mg iron/g liver (dry weight; dw) are at increased risk of iron-induced toxicity such as cardiac disease, hepatic fibrosis, diabetes mellitus and death (Hoffbrand AV *et al.* 2003; Olivieri NF & Brittenham. 1997; Telfer PT *et al.* 2000). The current goal for chelation therapy in transfusion-dependent patients is to maintain an “optimal” body iron burden corresponding to hepatic storage concentrations of less than 7 mg/g dw (Olivieri NF & Brittenham. 1997). MRI scans will be performed at the screening/baseline, Week 26, and Week 52 (or early termination) visits, and will be transmitted to a central laboratory for interpretation and LIC calculation.

### **8.1.2 Secondary Efficacy Measures**

#### **8.1.2.1 Patient Reported Quality of Life**

##### **SF36:**

The SF-36 is a multi-purpose, short-form health survey with only 36 questions. It yields an 8-scale profile of functional health and well-being scores as well as psychometrically-based physical and mental health summary measures and a preference-based health utility index. It is a generic measure, as opposed to one that targets a specific age, disease, or treatment group. A sample of the questionnaire is included in Appendix 18.5. The SF-36 Questionnaire will be completed by patients aged 18 years old and above at the baseline, Week 26, and Week 52 (or early termination) visits.

##### **Child Health Questionnaire:**

The Child Health Questionnaire™ (CHQ) is a family of generic quality of life instruments that have been designed and normed for children. The CHQ measures 14 unique physical and psychosocial concepts. The versions to be used in this study are the Child Health Questionnaire-Parent Form 50 (CHQ-PF50), composed of 50 questions, and the Child Health Questionnaire Child Form 87 (CHQ-CF87), composed of 87 questions. Samples of the questionnaires are included in Appendix 18.5. When possible, both versions will be completed for patients aged 17 years and under at the baseline, Week 26, and Week 52 (or early termination) visits.

#### **8.1.2.2 Cardiac MRI T2\***

Myocardial MRI T2\* can be used to monitor the myocardial iron load resulting from chronic transfusions, with low T2\* levels reflecting a high cardiac iron concentration and high T2\* values reflecting low cardiac iron. This technique has been calibrated with cardiac iron concentration in post mortem hearts (Carpenter JP *et al.* 2011). Studies in non-iron-overloaded patients reveal that none have a cardiac T2\* <20 ms, a value that is

now widely used clinically as the threshold for cardiac iron overload (Wood JC. 2007). The ability of cardiac MRI T2\* to identify patients at risk of iron-induced cardiac disease and premature death has been reported (Kirk P *et al.* 2009), and its predictive value has been prospectively evaluated in 652 transfusion-dependent thalassemia patients from 21 UK centers who had cardiac MRI T2\* assessment and who had their cardiac status followed over time (Kirk P *et al.* 2009). The results of that study demonstrated that the lower the cardiac MRI T2\* value (i.e., the higher the cardiac iron load), the higher the risk of developing iron-induced cardiac failure within the subsequent 12 months. MRI scans for the assessment of cardiac MRI T2\* will be performed at the screening/baseline, Week 26, and Week 52 (or early termination) visits, and will be transmitted to a central laboratory for interpretation.

#### 8.1.2.3 Serum Ferritin

The most commonly used method for the assessment of body iron burden is the measurement of serum ferritin concentration (Borgna-Pignatti C & Castriota-Scanderbeg. 1991; Brittenham GM *et al.* 1981; Brittenham GM *et al.* 1993; Finch C. 1994; Finch CA *et al.* 1986; Lipschitz DA *et al.* 1974; Worwood M *et al.* 1980). Ferritin is the major storage protein for iron. It is present in low concentrations in the plasma and is a reflection of total body iron. Due to the continual transfusional iron input and the lack of a natural excretory pathway for the excess iron, a progressive increase in serum ferritin concentration occurs in transfusion-dependent patients in the absence of effective iron chelation therapy. Sequential measures of serum ferritin concentration remain the most common method for assessment of body iron burden, and in clinical practice it is the standard for identifying trends in iron status within individuals and across populations. For an individual, serum ferritin is therefore a useful index of changes in iron load status, and for decades, a serum ferritin level above 2,500 µg/L has been considered an important indicator of the relative risk of death (Hoffbrand AV *et al.* 2003; Olivieri NF *et al.* 1994; Telfer PT *et al.* 2000). Serum ferritin will be assessed at baseline and at the Weeks 12, 26, 40 and 52 (or early termination) visits.

## 8.2 Safety

The Investigator is responsible for monitoring the safety of patients who have entered the study. Safety and tolerability of deferiprone will be assessed during the study by physical examinations, vital signs, clinical laboratory tests, spontaneous reporting of symptoms by patients, and by nurses' and physicians' observations.

#### 8.2.1 Medical History, Physical Examination, Vital Signs and Prior and Concomitant Medication Use

A medical history will be collected at screening/baseline, and reviewed at the end of study visit (Week 52 or early termination). A complete physical examination will be performed at screening/baseline, and Weeks 26 and 52 visits according to the schedule of events (Appendix 18.1).

- Vital signs (temperature, heart rate, respirations, blood pressure) and weight will be measured at screening/baseline, baseline and each monthly visit (Weeks 4, 8, 12, 16, 20, 26, 32, 36, 40, 44, 48 and 52 (or early termination)). Height will be measured only at screening/baseline, semi-annual and week 52 (or early termination) visits.
- Information about concomitant medications will be collected at screening/baseline, baseline and each monthly visit (Weeks 4, 8, 12, 16, 20, 26, 32, 36, 40, 44, 48 and 52 (or early termination)). The following must be recorded in the Source Documents and eCRFs:
  - All medications used during the 3 months prior to the screening/baseline visit;
  - Any previous use of deferiprone, deferoxamine and deferasirox;
  - Any medications that the patient continues to take during the trial;
  - Any medications which the patient starts to take during the trial.
  - The name, dose, route, frequency, indication, and start and stop dates of all medications used during the trial must be noted in the Source Documents and eCRFs as well as whether or not the medication was used to treat an medical events/adverse event.

### **8.2.2 Clinical Laboratory Tests**

Lab reports must be promptly interpreted by the Investigator. Any abnormal results should be assessed for clinical significance. Any clinically relevant abnormalities/changes which occur during the trial that are not part of a larger medical condition that is already recorded must be recorded on the source documents and the Adverse Events section of the eCRF.

The following clinical laboratory tests will be performed. Analyses will be performed at a central laboratory, with the exception of the weekly or biweekly hematology assessments, which may be performed at a local laboratory.

#### Hematology:

Hematology assessments consisting of hemoglobin, total WBC, ANC and platelets will be performed at screening/baseline, baseline, weekly after start of dosing until Week 26, and then biweekly until Week 52 (or early termination).

#### Biochemistry:

Biochemistry assessments will be performed at the screening/baseline visit and then monthly: Weeks 4, 8, 12, 16, 20, 26, 32, 36, 40, 44, 48 and 52 (or early termination). Biochemistry evaluation will consist of total protein; GGT; lactate dehydrogenase (LDH); sodium, potassium, chloride, glucose (fasting at screening and Week 52 or early termination visits only); total, direct and indirect bilirubin; AST; ALT; albumin; blood urea nitrogen; calcium; creatinine; uric acid; alkaline phosphatase; and amylase.

Serology:

Serology assessments will be performed at the screening/baseline, Week 26, and end of study (Week 52 or early termination) visits. Serology evaluation will consist of Hepatitis B and C and HIV testing.

Urinalysis:

Urinalysis assessments will be performed at the screening, Week 26, and end of study (Week 52 or early termination) visits. Urinalysis by urine dipstick will consist of pH, specific gravity, glucose, protein, ketones, and blood. If indicated by the dipstick results, sediment microscopy will be performed. If there is blood in the urine or three or more “plus signs” for protein, samples must be sent for microscopy.

Pregnancy Test:

Serum pregnancy tests will be performed at the screening/baseline and baseline visits and monthly (Weeks 4, 8, 12, 16, 20, 26, 32, 36, 40, 44, 48 and 52 (or early termination)). Urine pregnancy test will be performed at the baseline visit.

### **8.2.3 ECG**

A standard 12-lead ECG will be performed at the screening, Week 26, and end of study (Week 52 or early termination) visits. As a minimum, the following parameters will be assessed: HR, PR, QRS, QT, QTcF, and QTcB. Results will be interpreted by the Investigator. The overall interpretation will also be documented.

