If a patient withdraws early, he or she will return to the clinic for an Early Termination Visit as soon as possible, and no later than 1 month following treatment discontinuation. All of the efficacy and safety evaluations will be performed at the last study visit or the Early Termination visit, whichever comes first.

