## 4.5 Withdrawal Criteria

A patient has the right to withdraw from the study at any time and for any reason without consequence to future care by the Investigator or study center. The reason for withdrawal will be sought.

When a patient decides to withdraw from the study, he/she should always be contacted, not only to determine the reason(s) for withdrawing, but also to determine if there were any adverse events (AEs). Whenever possible, the patient should return for a clinic visit at the time of or soon after discontinuation of study medication but no later than 1 month after treatment discontinuation. All investigational products and materials should be returned. If any AEs occurred, the Investigator must attempt to follow up with the outcome for 30 days post-study withdrawal.

Data collected for patients who are withdrawn after receiving the study drug should be evaluated for efficacy and safety.

If, for any reason, the Investigator decides to withdraw a patient before completing the study, the reason for withdrawal must be entered into the source document and the electronic case report form (eCRF).

A patient may be withdrawn from the study at any time for any of the following reasons:

- Patient request;
- Medical reasons considered significant by the patient and/or Investigator;
- Requirement for concomitant medication that may interfere with the evaluation of study medication, or may be contraindicated;
- Occurrence of other illnesses that affect the patient's further participation in the study or evaluation of study medication;
- Significant changes in QTcF interval (defined as QTcF change of greater than 60 ms) are detected;
- Any other situation where, in the opinion of the Investigator, continuation of the study would not be in the best interest of the patient.

A patient **must** be withdrawn from the study if any of the following conditions apply:

- Pregnant or planning to become pregnant (see [Section 9.2](#) Procedures in Case of Pregnancy);
- Occurrence of any adverse reaction characterized as life-threatening or disabling;

- Non-compliance with blood counts. During the first 6 months, if a patient misses a weekly ANC monitoring visit, then missing a further 3 of the next 5 visits (i.e., a total of 4 out of 6) will result in automatic withdrawal. During the last 6 months, ANC monitoring will be done biweekly, and missing 3 consecutive biweekly blood counts will result in automatic withdrawal.

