## 5.10 Early Termination

Patients can be withdrawn from the study at any time. Reasons for withdrawal will be documented in the source document and eCRF, and early termination visit procedures should be performed within 1 month.

These data should be recorded and entered in the eCRF, as they constitute essential data from an evaluation that should be conducted prior to discharging any patient from the study.

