#### ECGs

Clinically significant 12-lead ECG abnormalities will be reported. The number and percentage of patients with normal and abnormal 12-lead ECG results will be provided for each scheduled visit.

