Dose reduction recommendations will be based on regular assessment of safety markers. Efficacy, safety and tolerability evaluations will occur according to the schedule of evaluation (Table 1). Rescue medication (intravenous administration of deferoxamine or combination of 2 iron chelators: Ferriprox, deferoxamine or deferasirox) for the treatment of iron overload will not be allowed during the Treatment Phase. Should iron overload symptoms become intolerable for the patient despite dose adjustment, the Investigator should withdraw the patient from the study.

If a patient withdraws early, he or she will return to the clinic for an Early Termination Visit as soon as possible, and no later than 1 month following treatment discontinuation.

All of the efficacy and safety evaluations will be performed at the last study visit or the Early Termination visit, whichever comes first.

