8.3 Vital Signs, Weight and Height

Descriptive statistics will be presented for temperature, resting heart rate, respiratory rate, systolic blood pressure, diastolic blood pressure, weight and height at each visit. Changes from baseline to each follow-up assessment will be also summarized using descriptive statistics by treatment group.

8.4 12-Lead ECG

ECG data will be summarized using descriptive statistics at each assessment by treatment group. Change from baseline to each follow-up assessment will be also summarized using descriptive statistics by treatment group. Shift tables for clinically significant abnormality between baseline and the last assessment will be constructed by treatment group.

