Note: Similar tables will be produced for PR (ms), QRS (ms), QT (ms), QTcF (ms), and QTcB (ms), respectively.

Data source: 16.2.9 Listing of 12-lead electrocardiogram

Table 14.3.5.3 Shift table for clinically significant abnormality for 12-lead ECG: Deferiprone group

	n (%)	Last Assessment		P-value (McNemar's test)
		Normal	Abnormal	
Baseline	Normal	xx (xx)	xx (xx)	0xxxx
	Abnormal	xx (xx)	xx (xx)	

P-value = Data source: 16.2.9 Listing of 12-lead electrocardiogram

Table 14.3.5.4 Shift table for clinically significant abnormality for 12-lead ECG: Deferoxamine group

	n (%)	Last Assessment		P-value (McNemar's test)
		Normal	Abnormal	
Baseline	Normal	xx (xx)	xx (xx)	0xxxx
	Abnormal	xx (xx)	xx (xx)	

P-value = Data source: 16.2.9 Listing of 12-lead electrocardiogram

Table 14.3.6.1.1 Hemoglobin at each assessment

	Treatment				P-value (T-test)
	Hemoglobin	Deferiprone		Deferoxamine	
Visit	N	Mean ± SD (Min, Max)	N	Mean ± SD (Min, Max)	0.xxxx
Baseline	xxx	xx.x ± xx.x (xx, xx)	xxx	xx.x ± xx.x (xx, xx)	0.xxxx
Week 1	xxx	xx.x ± xx.x (xx, xx)	xxx	xx.x ± xx.x (xx, xx)	0.xxxx
Week 2	xxx	xx.x ± xx.x (xx, xx)	xxx	xx.x ± xx.x (xx, xx)	0.xxxx
Week 3	xxx	xx.x ± xx.x (xx, xx)	xxx	xx.x ± xx.x (xx, xx)	0.xxxx
Week 4	xxx	xx.x ± xx.x (xx, xx)	xxx	xx.x ± xx.x (xx, xx)	0.xxxx
...
Week 49	xxx	xx.x ± xx.x (xx, xx)	xxx	xx.x ± xx.x (xx, xx)	0.xxxx
Week 50	xxx	xx.x ± xx.x (xx, xx)	xxx	xx.x ± xx.x (xx, xx)	0.xxxx
Week 51	xxx	xx.x ± xx.x (xx, xx)	xxx	xx.x ± xx.x (xx, xx)	0.xxxx
Week 52	xxx	xx.x ± xx.x (xx, xx)	xxx	xx.x ± xx.x (xx, xx)	0.xxxx

Note: Similar tables will be produced for total white blood cell (WBC), absolute neutrophil count (ANC), and platelets.

Data source: 16.2.11 Listing of hematology

Table 14.3.6.1.2 Change in hemoglobin at each follow-up assessment

	Treatment				
	Hemoglobin	Deferiprone		Deferoxamine	
Visit	N	Mean ± SD (Min, Max)	N	Mean ± SD (Min, Max)	0xxxx
Week 1	xxx	xx.x ± xx.x (xx, xx)	xxx	xx.x ± xx.x (xx, xx)	0xxxx
Week 2	xxx	xx.x ± xx.x (xx, xx)	xxx	xx.x ± xx.x (xx, xx)	0xxxx
Week 3	xxx	xx.x ± xx.x (xx, xx)	xxx	xx.x ± xx.x (xx, xx)	0xxxx
Week 4	xxx	xx.x ± xx.x (xx, xx)	xxx	xx.x ± xx.x (xx, xx)	0xxxx
...
Week 49	xxx	xx.x ± xx.x (xx, xx)	xxx	xx.x ± xx.x (xx, xx)	0xxxx
Week 50	xxx	xx.x ± xx.x (xx, xx)	xxx	xx.x ± xx.x (xx, xx)	0xxxx
Week 51	xxx	xx.x ± xx.x (xx, xx)	xxx	xx.x ± xx.x (xx, xx)	0xxxx
Week 52	xxx	xx.x ± xx.x (xx, xx)	xxx	xx.x ± xx.x (xx, xx)	0xxxx

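### The SAP's only categorical ECG table compares baseline with the last ECG and omits the by-visit normal/abnormal counts in the protocol, so it can understate on-treatment abnormalities (minor reporting point)

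*Protocol*

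**What the plan says.** **Schedule.** Protocol 8.2.3: "A standard 12-lead ECG will be performed at the screening, Week 26, and end of study (Week 52 or early termination) visits". Apart from any unscheduled ECG, a patient therefore has at most two post-baseline ECGs.

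**Protocol analysis.** The ECG paragraph of protocol 11.4.1.4 says: "The number and percentage of patients with normal and abnormal 12-lead ECG results will be provided for each scheduled visit". Protocol 11.2.3 lists the 12-lead ECG as a safety endpoint.

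**SAP analysis.** SAP 8.4 plans descriptive statistics at each assessment, descriptive statistics for change from baseline, and one categorical analysis: "Shift tables for clinically significant abnormality between baseline and the last assessment will be constructed by treatment group". The shells match this. Tables 14.3.5.1 and 14.3.5.2 show mean, SD, minimum and maximum for heart rate, PR, QRS, QT, QTcF and QTcB at Months 6 and 12. The categorical shell is "Table 14.3.5.3 Shift table for clinically significant abnormality for 12-lead ECG: Deferiprone group", with a twin, Table 14.3.5.4, for deferoxamine. Each is a two-by-two table of normal and abnormal with McNemar's test.

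**QTcF threshold.** Protocol 4.5 lists this among the reasons for which a patient may be withdrawn: "Significant changes in QTcF interval (defined as QTcF change of greater than 60 ms) are detected".

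**Early termination.** Protocol 5.10 says that "early termination visit procedures should be performed within 1 month". Protocol 3.2 asks for the "Early Termination Visit as soon as possible, and no later than 1 month following treatment discontinuation", and SAP 3.3 repeats the limit: "no later than 1 month following treatment discontinuation".

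**The concern.** A shift to the last ECG shows how patients ended, not whether an abnormality arose on drug. With only two scheduled post-baseline ECGs, the last one overrides the Week 26 reading for every patient who has both. For a withdrawn patient the last ECG may also be off drug. SAP 8.4 does not define the last assessment or tie it to exposure.

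The protocol's by-visit counts would have kept Week 26 visible, but the SAP does not specify them. At stake is whether the report's summary of ECG abnormalities, for a named safety endpoint, reflects what happened during treatment.

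**Working it through.** The plan states no figure on this point, so the check sets the provisions side by side.

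**1. By-visit counts.** The protocol wants n (%) normal and abnormal at each scheduled visit. No such table is in SAP 8.4, in the 14.3.5 table list or in the shells. The same SAP does plan the proportion abnormal at each assessment for hematology (Figure 14.3.1.2) and biochemistry (Figure 14.3.2.2).

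**2. How patients fall in the shift table.** Take patients who are normal at baseline:

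| Week 26 ECG | Last ECG | Cell in Table 14.3.5.3 or 14.3.5.4 |
|---|---|---|
| Normal | Normal | Normal-to-normal |
| Normal | Abnormal | Normal-to-abnormal |
| Abnormal | Abnormal | Normal-to-abnormal |
| Abnormal | Normal | Normal-to-normal |

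The fourth row is misplaced if the table is read as showing on-treatment abnormality. It can arise in a completer with no off-drug gap, or in a patient withdrawn after Week 26.

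**3. The off-drug gap.** Protocol 1.2 gives deferiprone an elimination half-life of 2 to 3 hours. With one month taken as 30 days, the limit is 30 × 24 / 3 = 240 to 30 × 24 / 2 = 360 half-lives. An ECG at that limit is off deferiprone. This says nothing about how fast an ECG finding resolves, and the documents give no such figure.

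**4. QTcF.** The by-visit tables give the mean, SD, minimum and maximum of QTcF and its change. No table counts patients with a change above 60 ms. Because protocol 4.5 makes withdrawal optional, a patient can cross the threshold, continue, and enter no threshold count.

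**5. Size.** Let A be the patients in an arm who are normal at baseline and abnormal at Week 26, and R those of them who are normal at the last ECG. The table shows A − R of them, so the understatement is R, anywhere from 0 to A. The documents give neither A nor R.

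**6. A wholly hypothetical illustration.** Only the 142 comes from the documents: it is the projected deferiprone total in the SAP sample-size section. It includes withdrawn patients, so fewer would have a Week 26 ECG. Suppose all are normal at baseline and 5% are abnormal on treatment: 0.05 × 142 = 7.1, about 7. If roughly 25%, 50% or 75% of the 7 are normal at the last ECG (2, 4 or 5 in whole patients), the table shows 5, 3 or 2. With b normal-to-abnormal shifts and none the other way, the exact two-sided McNemar p is 2 × 0.5^b:

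- b = 7: 0.016
- b = 5: 0.063
- b = 3: 0.25
- b = 2: 0.50

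This shows the direction of the effect. It is not an estimate for this trial.

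**The case against.** The strongest reply is that other outputs carry these events.

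- Protocol 8.2.4.2 requires ECG abnormalities judged clinically significant to be recorded as AEs or SAEs if they meet the definition and are not part of a condition already recorded. AEs are counted per arm over treatment (SAP 8.1, Table 14.3.1.2), and later recovery does not remove them.
- Withdrawals appear with reason and detail in Table 14.1.4, in the AE-withdrawal count of Table 14.3.1.1 and in Listing 16.2.34. ECGs are in Listing 16.2.9.
- One month is an outer limit. The visit is due as soon as possible, and protocol 3.2 allows the evaluations at the last study visit if that comes first.
- SAP 8 promises frequency tables for discrete safety data, and SAP 14 and 17 allow added tables and altered shells.
- Baseline-to-end shift tables are the protocol's own format for laboratory data.

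Most of this stands. A reader might infer that a Week 26 abnormality vanishes from the report, leaving only a by-visit maximum, or that QTcF withdrawals are counted nowhere. The AE and withdrawal outputs contradict both. Nor is the ECG schedule in protocol 8.2.3 an error.

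What does not stand is that these outputs replace the missing count. AE recording depends on the investigator's judgement of clinical significance, whereas the protocol's by-visit counts cover all abnormal results. Withdrawal tables cover only those withdrawn, and a listing is not a summary. The general SAP wording permits a by-visit ECG table but does not specify one.

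**Conclusion.** The point holds as a minor reporting improvement. The SAP omits a by-visit ECG count that the protocol specifies. The shift table it does specify can place an on-treatment abnormality in the normal-to-normal cell. No specified output gives n (%) per arm with any on-treatment ECG abnormality, or with a QTcF change above 60 ms. Those statements follow from the text alone.

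The size is unknown. It depends on how many patients are abnormal at Week 26 and normal at the last ECG, for which the documents give no basis. The point does not show that a safety signal would be missed in the report as a whole, and it does not touch the efficacy analysis.

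**What to change.** Change SAP 8.4, the 14.3.5 table list and the shells:

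1. Restore n (%) normal and abnormal per arm at Week 26 and Week 52, as the protocol's ECG paragraph specifies.
2. Base the abnormality shift on the worst on-treatment post-baseline ECG, including unscheduled ECGs where recorded. Show ECGs taken after the last dose separately, and define both categories by the last dose date.
3. Add n (%) per arm with a QTcF increase above 60 ms at any post-baseline ECG. The protocol speaks of a change, so the table should label the direction counted.

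No new data are needed: Listing 16.2.9 is already the source for the ECG tables. The cost is SAP wording and one or two extra tables. No clinical rule changes.
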